Another factor that complicates prevalence estimates of aTB is that various screening and diagnostic algorithms are currently in use. Most prevalence surveys use either the presence of symptoms or lung field abnormality on chest x-ray to trigger collection of sputum, which is then subjected to NAAT. Because of its cost and requirement for laboratory infrastructure, sputum MGIT is rarely performed at scale, but when it is, it identifies additional cases of bacteriologically-confirmed TB¹⁴.

The efficiency of chest x-ray surveys to detect asymptomatic TB has been greatly enhanced by the development of portable hardware for the capture of high-quality digital chest x-ray images and the development of computer-assisted diagnostic algorithms that can identify lung field abnormalities suggestive of TB with comparable accuracy to human radiologists^{15, 16}. Despite their efficiency, surveys in which sputum collection is triggered by chest x-ray, fail to detect the subpopulation of people with asymptomatic TB who have normal chest x-rays (recently shown by Mendelsohn et al. to comprise up to 43% of asymptomatic bacteriologically-confirmed TB among household contacts of a symptomatic index case)¹⁷. Chest x-ray screening surveys also identify people with chest x-rays suggestive of TB whose screening sputum tests are negative. This group presents a diagnostic and management challenge to health systems because the chest x-ray abnormalities of people in this group may be attributable to early progressive TB, inactive previously treated TB, non-TB infectious or non-infectious aetiologies. The stochasticity of sputum sampling and the limited sensitivity of sputum Xpert and MGIT for paucibacillary TB, means that collection of additional sputum samples for microbiologic evaluation would confirm TB-C in a proportion of these individuals. This knowledge and information about the proportion of the remaining TB-U group that progressed to bacteriologically-confirmed TB in the year after screening is important unknown information to guide future screening efforts. Addressing key knowledge gaps about the comparative performance of existing diagnostic tests to identify aTB and the characteristics and outcomes of sub-groups identified by different combinations of these tests can be addressed through a large-scale screening study that collects sputum for Xpert and MGIT and dCXR on all participants.

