		
3. Participants selected as healthy controls
 
Inclusion criteria
 
 1. Adolescent/adult participant in TB screening 2. Screening W4SS negative 3. Screening sputum Xpert negative; AND Mtb MGIT negative* 4. Selected as a healthy control in the Cross-sectional study of Mtb infection in households (see above) 
ALL 3 groups above
 
Exclusion criteria
 
 1. Unable or unwilling to consent 
* MGIT results returning after enrolment may result in study group re-categorisation

Cohort study (sub-study 2)	Adolescents and adults (≥ 15 years) who participated in TB screening.	
Participants who meet the study case definition for bacteriologically-unconfirmed TB (TB-U)
 
Inclusion criteria:
 
 1. Adolescent/adult participant in TB screening 2. All three sputa Xpert are negative/ ‘trace’ AND all three sputum are Mtb MGIT negative 3. Screening dCXR/CAD interpretation is “suggestive of TB” 4. Clinical assessment at phenotyping visit does not suggest a non-TB aetiology for dCXR/CAD findings and is consistent with TB-U 5. Participant did not commence TB treatment after phenotyping visit 
Exclusion criteria
 
 1. Unable or unwilling to consent to longitudinal follow-up

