3.8 STUDY OUTCOMES/ ANALYSES

The study is designed to assess both the transmission of Mtb within households and the diagnostic performance of current and novel tools for detecting asymptomatic TB. The outcomes are grouped into primary and additional outcomes categories as outlined below.

CORE STUDY

Primary endpoint: Cumulative prevalence of child household contact IGRA positivity or confirmed TB (TB-C) at 10 weeks after diagnosis of the index case.

Additional outcomes/ analyses:

- (1) Proportion of children that convert from negative IGRA status at baseline to a positive IGRA status at 10-week visit.
- (2) Proportion of children with a positive plasma cell free Mtb DNA assay and positive Mtb-specific T cell activation assay, stratified by household group.
- (3) Whole genome sequencing of Mtb isolates from people with TB-C and household contacts.

CASE-CONTROL PHENOTYPING STUDY (SUB-STUDY 1)

- (4) Sensitivity, specificity, positive predictive value, negative predictive value, yield, feasibility, acceptability of digital chest x-ray with computer aided diagnosis (dCXR/CAD), sputum Nucleic Acid Amplification Test (NAAT), Mycobacteria Growth Indicator Tube (MGIT), tongue swab NAAT, and bioaerosol collection facemask mask NAAT to detect aTB-C.
- (5) Symptoms, health outcomes quality of life, comorbidities, nutritional status, and TB history, relative to group and W4SS status at screening.

(6) Proportion and characteristics of participants with detectable exhaled breath condensate lipoarabinomannan (LAM), positive plasma cell free Mtb DNA assay, positive Mtb-specific T cell activation assay and additional blood-based TB biomarkers, stratified by group.

TB UNCONFIRMED (TB-U) COHORT (SUB-STUDY 2)

(7) Time to event and factors associated with microbiological or clinical progression in participants with initially untreated aTB-U.

(8) Plasma biomarkers (including cell free Mtb DNA, Mtb-specific T cells, transcriptional signatures) that correlate with progression from aTB-U in the 12 months after TB screening

(9) Proportion and characteristics of participants with TB screening results suggestive of (TB-U) who have a subsequent positive sputum GeneXpert Ultra, sputum MGIT, tongue swab NAAT or Bioaerosol collection facemask mask NAAT.

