5. STATISTICAL CONSIDERATIONS AND MODELLING

5.1 SAMPLE SIZE CALCULATIONS

CORE STUDY

The core study has two co-primary objectives: (1) to compare IGRA positivity in child household contacts of participants with aTB-C with that of community controls; (2) to compare IGRA positivity in child household contacts of participants with aTB-C cases with that of participants with sTB-c. We are using child IGRA positivity as a proxy measure of TB transmission.

Based on our existing data on the prevalence of aTB-C in each setting, we expect to screen 60,000 individuals in Bandung and 30,000 in KwaZulu Natal to identify 150 cases of aTB (**Table 3**). We expect ~20% of children to be IGRA positive in control households in Bandung and 7% to be positive in KwaZulu Natal, and an average of 1.5 (SD=0.7) and 2.5 (SD=1.6) children per household, respectively, in each setting. We have assumed an intra-cluster correlation coefficient (ICC) of 0.20-0.30 in each setting, based on our data in KwaZulu Natal⁶⁴.

Table 3: Assumptions used to determine overall scale of screening and power for the asymptomatic TB transmission in Indonesia and South Africa study

Parameter	Indonesia	South Africa
Number screened	60,000	30,000
Asymptomatic TB prevalence (Clinical -, CXR positive, micro +/-)	0.25%	0.50%
Number of asymptomatic TB cases detected	150	150
Number of control HH	300	300

IGRA positivity in children aged 2-14 years	STB index HH: 40% Control HH: 20%	STB index HH: 18% Control HH: 7%
Household size (children aged 2-14 years)	Mean = 1.5 SD = 0.7	Mean = 2.5 SD = 1.6
Intra cluster correlation (ICC)	0.20 to 0.30	0.20 to 0.30

For our first co-primary objective, we have used the absolute risk difference in child IGRA positivity (rather than the risk ratio) as our effect estimate of interest, because of the difference in duration of exposure (lifetime exposure to community transmission for children in control households, vs a relatively short duration of exposure to the index case for children in aTB-C households).

If the true risk difference between IGRA positivity in aTB-C households compared to control households is 10-15%, inclusion of 150 aTB-C households and 300 control households will provide $\geq 90\%$ power to detect a significant difference in household IGRA positivity between these groups. We will have 80% power to detect a minimum difference of 12% in Bandung and 7% in KwaZulu Natal ([Table 4](#)).

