Table 4: Minimum risk difference that can be detected in each site with 80% power, comparing aTB and control households

Number aTB cases	Number controls ¹	Mean children per HH	ICC	% IGRA positive in control HH	% IGRA positive in aTB HH	Risk difference ²	Power
Indonesia							
150	300	1.5	0.30	20%	32%	12%	80%
South Africa							
150	300	2.5	0.30	7%	14%	7%	80%

¹Number of control households. ²Absolute difference = proportion of children IGRA+ in aTB households minus proportion of children IGRA+ in control.

For our second co-primary objective, we have used the risk ratio (relative risk) as the effect estimate of interest, because the duration of exposure for children in aTB-C and sTB-C households is expected to be similar. For policy decisions, it would be useful to know that the transmission risk of aTB-C is not substantially lower than that of sTB-C; therefore, we have used a non-inferiority approach for our power calculations. We have assumed that the prevalence of IGRA positivity in children in sTB-C households is 40% in Bandung and 18% in KwaZulu Natal (our best estimates, based on available data). With 150 sTB-C and 150 aTB-C index cases, we will have at least 80% power in each setting to demonstrate that the transmission risk with aTB-C is not less than 50% compared with that of sTB-C, assuming that the true risk ratio (RR) is at least 0.90 ([Table 5](#)).

Table 5: Relative reduction that can be excluded with 80% power, comparing aTB and sTB households¹

Number sTB cases	Number aTB cases	% IGRA positive in sTB HH	% IGRA positive in aTB HH	Risk ratio (aTB/sTB)	Relative reduction that can be excluded ²
Indonesia - aTB vs sTB					
150	150	40%	28%	0.70	0.46
150	150	40%	32%	0.80	0.55
150	150	40%	36%	0.90	0.63
South Africa - aTB vs sTB					
150	150	18%	12.6%	0.70	0.43
150	150	18%	14.4%	0.80	0.49
150	150	18%	16.2%	0.90	0.55

¹Assuming ICC=0.30. ²Lower limit of 95% confidence interval for risk ratio

CASE-CONTROL STUDY (SUB-STUDY 1)

The case-control study will enrol 150 aTB-C and 150 sTB-C cases, and 300 community controls with no TB. Assuming that the true sensitivity and specificity of the Plus Life tongue swab and bioaerosol collection facemask diagnostic tools are between 70-95%, with 150 aTB-C and 150 sTB-C cases, we will be able to estimate the sensitivity with a precision of $\pm 7.6\%$ to $\pm 4.0\%$. With 300 controls, we will be able to estimate the specificity with a precision of $\pm 5.3\%$ to $\pm 2.6\%$.

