Sensitivity analyses: In a high TB incidence setting, IGRA positivity in household members may be result of contact with infected individuals outside the household, rather than with the index case. This would lead to outcome misclassification since the assumption underlying our analysis is that IGRA-positivity is

a result of exposure to the index case. This effect should be non-differential so would bias estimates towards the null. We will conduct sensitivity analyses restricted to younger children (e.g. aged <10 years), with the assumption that younger children are more likely to have been infected by the household index case than through community or non-household contact. Additionally, quantitative bias analyses will be performed using alternate definitions of 'asymptomatic' and 'symptomatic' TB-C index cases to account for 'misclassification' between these groups based on discrepancies between W4SS status at screening and the additional blinded symptom data collected at Visit 1.1.

CASE CONTROL STUDY (SUB-STUDY 1)

We will assess the performance of the standard and novel tools for diagnosing aTB-C and sTB-C by calculating the sensitivity, specificity, PPV, NPV and yield, and 95% confidence intervals, of each tool. We will use ROC curves and Chi-squared tests to explore the association of tool performance with child household contact IGRA positivity, to assess the ability of these tools to identify individuals with aTB who contribute to Mtb transmission.

We will compare bioaerosol status between aTB and sTB index cases and controls. Bioaerosol measurements will also be compared with tongue swab NAAT results. We will also explore their association with child IGRA positivity, to assess their performance as a surrogate for Mtb household transmission.

TB UNCONFIRMED (TB-U)COHORT STUDY (SUB-STUDY 2)

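### Sub-study 1 places predictive values, yield and standard-tool specificity in a case-control sample, where they reflect the sampling ratio and the way controls are selected, not screening

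*Protocol*

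**What the plan says.** Section 5.2, under the case-control heading, assesses the standard and novel tools for aTB-C and sTB-C by "calculating the sensitivity, specificity, PPV, NPV and yield, and 95% confidence intervals, of each tool". Outcome (4), listed under sub-study 1 in Section 3.8 and in the Protocol Summary, opens "Sensitivity, specificity, positive predictive value, negative predictive value, yield, feasibility, acceptability of digital chest x-ray with computer aided diagnosis (dCXR/CAD), sputum" and goes on to NAAT, MGIT, tongue swab and facemask, with aTB-C as the target.

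Section 5.1 fixes the sample: "The case-control study will enrol 150 aTB-C and 150 sTB-C cases, and 300 community controls with no TB". The Protocol Summary makes clear that this is per setting.

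Controls are drawn at random from noTB participants near an aTB-C household (Section 3.5). Table 1 requires them to be W4SS negative and "Screening sputum Xpert negative; AND Mtb MGIT negative", with re-categorisation on later MGIT results. The noTB screening group and the noTB case definition also require a normal X-ray. A confirmed case is defined by Xpert above trace, or a positive MGIT, on any of three sputa.

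Table 3 assumes an aTB prevalence of 0.25% in Indonesia and 0.50% in South Africa. The Background describes the design as "a large-scale screening study that collects sputum for Xpert and MGIT and dCXR on all participants".

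**The concern.** PPV, NPV and yield depend on how common the disease is in the group tested. Here that frequency is set by the enrolment ratio. Values computed in this sample describe the ratio, and a reader would take them for the performance of a screening tool.

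Specificity raises a second problem. Two of the standard tools, and in effect a third, decide who may be a control, so a false positive on them removes the person from the denominator. Xpert and MGIT also decide who is a case, so their sensitivity carries incorporation bias.

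Secondary objective 1 (current tools) and secondary objective 2 (novel tools) are at stake. Section 6 also plans to simulate screening with current and novel tools. The Protocol does not say which accuracy values will enter the models, but a specificity of 100% fixed by selection would remove the false-positive burden from any scenario that used it.

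**Working it through.** **The plan's own figure.** Section 5.1 assumes that the swab and facemask "diagnostic tools are between 70-95%, with 150 aTB-C and 150 sTB-C cases" and states precision of ±7.6% to ±4.0% for sensitivity (n = 150) and ±5.3% to ±2.6% for specificity (n = 300). Exact Clopper-Pearson half-widths at 70% and 95% are 7.61% and 3.85% (n = 150), and 5.33% and 2.64% (n = 300). The figures reproduce, apart from 3.85 being printed as 4.0. The precision arithmetic is not at fault.

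**Inputs.** 150 aTB-C cases and 300 controls (Section 5.1); prevalence q = 0.0025 or 0.0050 (Table 3); 60,000 and 30,000 screened (Table 3). Sensitivity of 80% and specificity of 95% are illustrative values inside the Protocol's range.

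**In-sample values, aTB-C against controls.**
- PPV = 0.80×150 / (0.80×150 + 0.05×300) = 120/135 = 88.9%.
- NPV = 285/(285 + 30) = 90.5%.

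**Same tool in screening.** PPV = 0.80q / (0.80q + 0.05(1 − q)).
- Bandung: 60,000 screened, 150 cases, 120 true positives, 0.05×59,850 = about 2,990 false positives. PPV = 3.9%, NPV = 99.95%.
- KwaZulu-Natal: 30,000 screened, 150 cases, 120 true positives, 0.05×29,850 = about 1,490 false positives. PPV = 7.4%, NPV = 99.89%.

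**Across the Protocol's range (aTB-C, 150:300).**

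| Sensitivity / specificity | In-sample PPV | Bandung PPV (ratio) | KwaZulu-Natal PPV (ratio) |
|---|---|---|---|
| 70% / 70% | 53.8% | 0.58% (93×) | 1.16% (47×) |
| 95% / 95% | 90.5% | 4.5% (19.9×) | 8.7% (10.4×) |
| 95% / 99% | 97.9% | 19.2% (5.1×) | 32.3% (3.0×) |

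The first two rows span the Protocol's 70-95%; the third lies above it. The ratio drops below ten once specificity passes about 95.2-96.5% in KwaZulu-Natal and 97.7-98.3% in Bandung, depending on sensitivity.

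**Any confirmed TB as target.** The Protocol gives no total TB-C prevalence. If 50.4% of TB is asymptomatic (the Background's survey review), the totals are 0.25/0.504 = 0.50% and 0.50/0.504 = 0.99%. At 95%/95%, a 300:300 sample gives a PPV of 95.0%, against 8.65% in Bandung (11.0×) and 16.0% in KwaZulu-Natal (5.9×).

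**Specificity of the standard tools.** A control who turns out positive on Xpert or MGIT no longer meets the noTB definition. Among retained controls the count is 300/300 = 100%. The nominal exact 95% lower limit of 98.8% carries no information, because no other result was possible. In-sample PPV of Xpert and MGIT is then also 100% by definition.

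**Conflict within the document.** Section 5.1 ties the precision claim, including "With 300 controls, we will be able to estimate the specificity with a precision of" ±5.3% to ±2.6%, to tongue swab and facemask. The Protocol Summary makes the same claim for the diagnostic tools in general. For Xpert and MGIT that precision cannot apply.

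**The case against.** The strongest reply is that no sentence says the values will be left unweighted. Yield suggests a screening denominator, the Background points to the full screening study for comparing existing tests, and weighting may be set out in the SAP, which was not available. This has some force. But Sections 3.8 and 5.2 both assign these metrics to the case-control sub-study, and no other section plans them in the screened population. Weighting the controls also cannot bring back false positives that the control definition excludes.

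A reader might infer that PPV is inflated more than tenfold for every tool. The documents do not support that. It holds for aTB-C at specificity up to about 95%. The tongue swab section of the Background cites specificities of 100% in several studies, and for any confirmed TB in KwaZulu-Natal the factor can be below ten within the assumed range.

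A reader might also infer that all three standard tools have exactly 100% specificity. For X-ray this is not established. Table 1's control criteria contain no X-ray item, so the requirement rests on the noTB definitions. The text does not say how a film flagged by CAD but overruled by the radiologist is classed. If such a person counts as normal, some CAD false positives remain among the controls.

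Nor is sputum sensitivity wholly circular. The reference is any of three sputa by either of two tests, and a single Xpert or MGIT can miss cases in it. The bias is real but partial.

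Finally, it is tempting to repair novel-tool specificity by pooling TB-U participants with the controls. That would count as disease-free people whom the Protocol regards as having unconfirmed TB and expects to progress at about 10% a year. It would still miss symptomatic, sputum-negative people with normal X-rays, who fit none of the five screening groups and have no planned phenotyping visit unless culture turns positive.

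**Conclusion.** The point stands in limited form. Followed as written, Section 5.2 and outcome (4) give predictive values and yield governed by the enrolment ratio, and a specificity for Xpert and MGIT that cannot be estimated from these controls. For dCXR/CAD, specificity is fixed or nearly so. Novel-tool specificity can be estimated but is likely optimistic, because controls are asymptomatic with normal X-rays.

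For aTB-C the PPV inflation is 10.4 to 93 times over the Protocol's 70-95% range in a 150:300 comparison, and about 3-7 times at 99% specificity. This rests on Table 3's prevalences. That row is labelled "Asymptomatic TB prevalence (Clinical -, CXR positive, micro" positive or negative, so it may not be pure aTB-C prevalence, although the 150 aTB-C cases are derived from it.

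A reader might take this as a threat to the trial's main result. It is not: the co-primary comparisons of child IGRA positivity and their sample size do not use these estimates. The point concerns secondary objectives and should be corrected before those analyses are run.

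**What to change.** Amend Section 5.2 and outcome (4), in Section 3.8 and the Protocol Summary, as follows.

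1. **Standard tools.** Estimate accuracy, PPV, NPV and yield of dCXR/CAD and sputum Xpert in all screened participants with a valid screening sputum result: Xpert against MGIT, and dCXR/CAD against the bacteriological result. Report the swab-only group separately, since those who cannot or will not give sputum have no screening Xpert or MGIT. Do not report MGIT specificity against a reference that includes MGIT. State how CAD-positive films overruled by the radiologist are counted.
2. **Novel tools.** Report sensitivity and specificity from the sub-study, and say that specificity comes from asymptomatic, X-ray-normal controls and is likely optimistic. Show positivity in TB-U participants as a separate sensitivity analysis, not pooled with controls. Derive PPV and NPV by Bayes at the observed screening prevalence in each setting.
3. **Precision statement.** Limit the specificity precision in the Protocol Summary to the novel tools, as Section 5.1 already does.

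The cost is a change of analysis wording, with no new samples or visits. Reported predictive values will be less favourable. Measuring Xpert against MGIT departs from the composite case definition, so Xpert-positive, culture-negative people will count as false positives; this should be stated. Novel-tool specificity in symptomatic people with normal X-rays will remain unknown.

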5.2 ANALYTICAL APPROACH

Descriptive statistics will be used to summarise participant characteristics separately for each study setting, including household-level characteristics (e.g. socioeconomic status, household construction, number of household members), index-case level characteristics (e.g. age, sex) and child-level characteristics. The analyses for each endpoint will be conducted separately for each setting.

CORE STUDY

Comparison of aTB and control households: For the primary analysis, we will use random-effects logistic regression with a fixed effect for exposure group (aTB vs control) and a random intercept for household. Since control houses will be selected from the same neighbourhood as the aTB index cases, we will also include a random effect for matched set. From the fitted model, we will estimate the marginal risk difference in the proportion IGRA positive between the two groups.

Matching on neighbourhood will provide some control of confounding by neighbourhood-level factors (e.g. socioeconomic status, background exposure in the community). However, we will also conduct multivariable analyses, explicitly controlling for confounding using child-level (e.g. age, sex and degree of contact with index, such as sleeping in same room etc) and household-level covariates (e.g. household crowding). Covariate adjustment will be guided by theoretical causal diagrams, defined *a priori*.

Comparison of aTB and sTB households: For the primary analysis, we will use random-effects logistic regression with a fixed effect for TB exposure group (aTB vs sTB) and a random intercept for household. The marginal risk ratio will be estimated from the fitted model.

We will also conduct multivariable analyses, controlling for confounding using child-level, index case-level (age, sex, HIV status) and household-level covariates, as described above, with covariate adjustment guided by theoretical causal diagrams, defined *a priori*. If there is evidence of a difference in the infectiousness of aTB compared with sTB we will explore whether this is mediated through characteristics of index case disease severity (bacillary burden, cavitation etc) or other mechanisms.

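### Sub-study 1 tests the index adult's tool result against child IGRA status with ordinary Chi-squared tests and ROC curves, naming no household term and no unit of analysis; on a per-child reading the 5% error rate becomes about 7-8% in Bandung and 11-14% in KwaZulu-Natal

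*Protocol*

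**What the plan says.** Section 5.2, under the case-control study, names the method for linking diagnostic tools to transmission: "We will use ROC curves and Chi-squared tests to explore the association of tool performance with child household contact IGRA positivity". The stated aim is to learn which tools pick out people with asymptomatic TB who pass infection on. A second analysis of the same kind follows for bioaerosol measurements, with no method named: "We will also explore their association with child IGRA positivity, to assess their performance as a surrogate for Mtb household transmission". Neither sentence says whether the row of data is a child or a household, and neither mentions clustering.

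Elsewhere the protocol treats the same child outcome as clustered. Section 5.1 says "We have assumed an intra-cluster correlation coefficient (ICC) of 0.20-0.30 in each setting", with "an average of 1.5 (SD=0.7) and 2.5 (SD=1.6) children per household, respectively, in each setting" (Bandung first). In section 5.2 the core comparison of asymptomatic with symptomatic households uses "random-effects logistic regression with a fixed effect for TB exposure group (aTB vs sTB) and a random intercept for household", and the comparison with control households also has a household random intercept. Section 5.2 adds: "The analyses for each endpoint will be conducted separately for each setting".

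**The concern.** A tool result belongs to the index adult, so it is identical for every child in that household. When the explanatory variable is constant within a cluster and the outcome is correlated within it, a test that counts each child as an independent observation understates the variance by the full design effect. P-values come out too small and intervals too narrow.

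At stake is the evidence on which tools mark infectious people. Too many tools could appear to be associated with child infection, chiefly in KwaZulu-Natal, where households are larger and more variable. Because each setting is analysed on its own, the smaller inflation in Bandung does not dilute the larger one.

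**Working it through.** **Inputs**
- Children per household (section 5.1, Table 3): Bandung mean m = 1.5, SD 0.7; KwaZulu-Natal m = 2.5, SD 1.6.
- ICC (section 5.1, Table 3): 0.20 to 0.30 in both settings. The protocol says it is based on KwaZulu-Natal data, so for Bandung it is borrowed.
- Level of the test: two-sided 5%. This is an assumption; section 5.2 gives 95% intervals for the accuracy measures but no level for this test.
- Unit of analysis: the child. This is a reading, taken up under the objection.

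**1. Check against the plan's own figure.** The protocol states no error rate for this analysis. The nearest figure resting on the same inputs is the KwaZulu-Natal row of Table 4: 150 against 300 households, 14% against 7% IGRA positive, ICC 0.30, power 80%.
- Design effect: DE = 1 + [m(1 + CV²) − 1] × ICC, with CV = SD/m. Here CV = 1.6/2.5 = 0.64, m(1 + CV²) = 2.5 × 1.4096 = 3.524, so DE = 1 + 2.524 × 0.30 = 1.757.
- Effective numbers of children: 150 × 2.5/1.757 = 213.4 and 300 × 2.5/1.757 = 426.8.
- Pooled proportion (14% + 2 × 7%)/3 = 9.33%; standard error 0.0244 under the null and 0.0268 under the alternative.
- Power = Φ[(0.07 − 1.96 × 0.0244)/0.0268] = 79.7%, against 80% stated.

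So this design effect matches the planning in the setting where it matters most. The Bandung row does not reproduce: the same method gives 85.9% against the stated 80%. The stated value is the more cautious one, and nothing below depends on it.

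**2. Design effects with the stated SDs.**
- Bandung: CV = 0.7/1.5 = 0.467; m(1 + CV²) = 1.827; DE = 1 + 0.827 × 0.20 = 1.165 and 1 + 0.827 × 0.30 = 1.248.
- KwaZulu-Natal: DE = 1 + 2.524 × 0.20 = 1.505 and 1.757 as above.

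**3. Actual type I error** of an unadjusted 5% test = 2[1 − Φ(1.96/√DE)]. An unadjusted interval is too narrow by 1 − 1/√DE.

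| Setting | ICC | DE | 1.96/√DE | Type I error | Interval too narrow by |
|---|---|---|---|---|---|
| Bandung | 0.20 | 1.165 | 1.816 | 6.9% | 7% |
| Bandung | 0.30 | 1.248 | 1.754 | 7.9% | 10% |
| KwaZulu-Natal | 0.20 | 1.505 | 1.598 | 11.0% | 18% |
| KwaZulu-Natal | 0.30 | 1.757 | 1.479 | 13.9% | 25% |

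The design effect depends on household size and ICC, not on the number of households, so using cases only or cases plus controls does not change these figures.

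**4. Sensitivity to equal household sizes.** Setting the SD to zero, contrary to the protocol, gives DE = 1 + (m − 1) × ICC: 1.10-1.15 in Bandung (type I error 6.2-6.8%) and 1.30-1.45 in KwaZulu-Natal (8.6-10.4%).

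**5. Simulation.** Beta-binomial data with variable household size, 150 or 300 households and 20,000 runs per cell. The simulation assumed tool positivity of 70% and IGRA positivity of 32% (Bandung) and 16% (KwaZulu-Natal). The child-level Chi-squared test rejected in 7.0-8.1% of runs in Bandung and 10.9-14.0% in KwaZulu-Natal. With one row per household (any child positive), the same test rejected in 4.8-5.1%, which isolates clustering as the cause.

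**The case against.** The strongest objection is that the protocol does not state the unit of analysis. The aim concerns index individuals and there is one tool result per index, so one row per household would suit it, and step 5 shows that such a Chi-squared test holds its level. This stands: a reader might infer that the protocol commits itself to treating siblings as independent, but the text does not say so. The inflation belongs to the per-child reading. That is still the plainer reading, since the sentence names child contacts' IGRA positivity and the core outcome is analysed per child. If households were meant, the protocol needs to say so.

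A second objection is that variance estimation for exploratory work can be left to the SAP, and that the authors plainly know about clustering. This stands in part. It limits the weight of the point. But the protocol does not leave the method open; it names a test, and on the per-child reading that test is not valid for these data.

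A third is that ROC curves are not invalidated by clustering. This stands in full. The error rates above describe the Chi-squared test only. Clustering leaves the curve and the AUC point estimate in place, and section 5.2 specifies no AUC interval or test for this analysis.

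**Conclusion.** The point holds in a limited form. If children are the unit, the named Chi-squared test has an actual type I error of about 7-8% in Bandung and 11-14% in KwaZulu-Natal instead of 5%, and unadjusted intervals are about 7-10% and 18-25% too narrow. This rests on the per-child reading, an assumed two-sided 5% level, the protocol's household sizes and SDs, and its ICC range, which for Bandung is borrowed.

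Two stronger inferences are not supported. The square root of the design effect might be read as intervals up to 33% too narrow; 33% is how much wider the correct interval is (√1.757 = 1.33), and the shortfall of the unadjusted one is 25%. Nor does this reach the co-primary comparisons: both carry a household random intercept, and no sample size rests on the sub-study 1 test.

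**What to change.** In section 5.2, sub-study 1, state the unit of analysis and choose one of two routes:
- Child as the unit: replace the Chi-squared test with the household random-intercept logistic model already specified for the core study, with tool result as the fixed effect, or use a cluster-robust test.
- Household as the unit: define one outcome per index (for example, any child IGRA positive) and keep the Chi-squared test.

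In either case, obtain any AUC interval by resampling whole households, and apply the same rule to the analysis of bioaerosol results against child IGRA status.

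The cost is a sentence of text and little analysis work; no new data are needed. Child-level intervals become wider than unadjusted ones by √DE − 1, about 8-12% in Bandung and 23-33% in KwaZulu-Natal. The household route gives up the information on how many children in a household are positive.
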